4.3.3.4 Patient-Rated Wrist Evaluation

Descriptive statistics will be provided at each visit for the actual value and change versus baseline (HD) for the following variables:

- Total pain score
- Total function score
- Total score

All subscores for pain and function will be listed.

4.4 Safety Analysis

The analysis of all safety data will be performed on the SAF.

4.4.1 Adverse Events

The analysis of adverse events will consist of:

- An overview of treatment-emergent adverse events consisting of:
 - Any TEAE
 - Any serious TEAE
 - Any NVDX3-related TEAE
 - Any NVDX3-related serious TEAE
 - Any TEAE related to the grafting surgery, including the applied medical device
 - Any TEAE related to other study procedure
 - Any unexpected TEAE
 - Any unexpected serious TEAE
 - Any severe TEAE
 - Any severe serious TEAE
 - Any treatment-emergent AESI
 - Any treatment-emergent rAESI
- Frequency distributions and total number of events for patients with any TEAE by MedDRA SOC and by MedDRA SOC and PT.
- Frequency distributions and total number of events for patients with any NVDX3-related TEAE by MedDRA SOC and by MedDRA SOC and PT.
- Frequency distributions and total number of events for patients with any TEAE by MedDRA SOC and by MedDRA SOC and PT, and maximal severity.

Frequency distributions will be provided for the entire study period (all treatment-emergent events), and broken down into IS till 6 weeks post-IS (V5 included) (acute events) and beyond 6 weeks post-IS (V5 excluded) till study completion (completion V8 or early termination whichever comes first) (mid-term).

Separate listings will be provided for:

- Non-Treatment-Emergent AEs
- Acute or Mid-term TEAEs
- Serious TEAEs
- TEAEs of special interest

4.4.2 Safety Assessment by Local Radiologist

These data will be listed.

4.4.3 Laboratory Data

These data will be listed only.

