#### Secondary Endpoints

##### **Safety**

1. Description of all acute SAEs and NVDX3 related AEs between screening (V1) and 6 weeks post-IS (V5).
2. Description of all SAEs and NVDX3 related AEs beyond 6 weeks (V5 excluded) until 12 months post-IS
3. Description of Treatment Emergent AEs (TEAEs) for the periods:
  - a. Between screening and week 6 (V5 included)
  - b. Between week 6 (V5 excluded) till month 12 (V8 included)
  - c. Full study duration
4. Description of related and unexpected (S)AEs between inclusion and study completion
5. Description of AE of Special Interest (AESI) between inclusion and study completion
6. Description of lab data and vital signs obtained between inclusion and study completion

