### 9.4. Description of statistical methods

#### 9.4.1. General Approach

Descriptive statistics will be used throughout all the analyses.

Continuous variables will be summarized using the mean, standard deviation, median, and range.

Categorical variables will be summarized using frequency counts and percentages.

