#### **9.4.3. Analysis of the secondary endpoint(s)**

The analysis of secondary endpoints will be described in the SAP (same for exploratory endpoints)

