1.3.2 Secondary Endpoints

1.3.2.1 Safety

- Description of all acute SAEs and NVDX3 related AEs between screening (V1) and 6 weeks post-IS (V5).
- Description of all Serious TEAEs and NVDX3 related TEAEs beyond 6 weeks (V5 excluded) until 12 months post-IS.
- Description of Treatment Emergent AEs (TEAEs) for the periods:
 - Between IS² and week 6 (V5 included)
 - Between week 6 (V5 excluded) till month 12 (V8 included)
 - Full study duration
- Description of related and unexpected AEs between inclusion* and study completion (TEAEs).
- Description of related and unexpected Serious AEs between inclusion* and study completion (serious TEAEs).
- Description of AEs of Special Interest between inclusion* and study completion (TEAESIs).
- Description of lab data and vital signs obtained between inclusion* and study completion.

*Inclusion refers to Implant Surgery, i.e. when the NVDX3 was implanted.

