3.4 Summary Statistics

Unless specified otherwise, the following summary statistics will be used to describe the data:

- For quantitative variables: mean, 95% confidence interval (CI) on the mean, standard deviation (SD), minimum, 1st quartile, median, 3rd quartile, range, maximum, number of available and number of missing observations.
- For categorical variables: number and percentage for each of the scores or categories, and the number of observations.

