4.4.4 Vital Signs

Descriptive statistics at every scheduled visit will be provided for:

- Height (cm)
- Weight (kg)
- BMI (kg/m²)
- Body temperature (°C)
- Pulse rate (beats/min)
- Respiratory rate (breaths/min)
- Mean systolic blood pressure (mmHg)

- Mean diastolic blood pressure (mmHg)

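### SAP 4.4.3 reports laboratory data, part of a secondary safety endpoint, as listings only: an undeclared departure from the protocol's general summary rule that could let a consistent sub-clinical shift be missed

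*SAP*

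**What the plan says.** The SAP keeps the protocol's secondary safety endpoint (SAP 1.3.2.1): "Description of lab data and vital signs obtained between inclusion* and study completion". Its two components are then handled differently. For laboratory data, SAP 4.4.3 says: "These data will be listed only". For vital signs, SAP 4.4.4 says: "Descriptive statistics at every scheduled visit will be provided for", and the list that follows includes height, which is measured at screening only.

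Protocol 9.4.1 states: "Descriptive statistics will be used throughout all the analyses". It adds: "Continuous variables will be summarized using the mean, standard deviation, median, and range". Individual listings are promised separately in Protocol 9.4.7. Protocol 9.4.3 leaves the analysis of secondary endpoints to the SAP. SAP 3.4 sets its default in these terms: "Unless specified otherwise, the following summary statistics will be used to describe the data".

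The schedule of activities makes safety laboratory tests mandatory at screening, hospital discharge (HD), W2 and W6. At M3, M6 and M12 they are done only when a safety issue occurs or is suspected. SAP 3.5 defines a baseline for efficacy only.

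**The concern.** Laboratory testing is the trial's stated means of watching a risk that the protocol itself names. Protocol 1.2.1 says immune reactions cannot be excluded for this allogeneic product and will be tracked through safety laboratory tests. Protocol 8.1.4 ties the blood tests up to W6 to acute toxicity.

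The adverse event tables cover only part of this. Under Protocol 8.1.7 an abnormal result becomes an adverse event if the Principal Investigator judges it clinically significant, and results associated with the underlying disease are excluded unless worse than expected. A modest change in the same direction in most patients, for example in CRP, white cells or liver enzymes, could stay below that threshold in every patient. It would then appear only as scattered entries in a listing, and no table in the plan would bring them together.

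**Working it through.** The plan gives no figure to reproduce: there is no hypothesis, alpha, power or SD. The check has three parts.

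**1. Is the departure real, and is it declared?**
- Protocol 9.4.1 is a general rule covering all analyses. It is not a commitment specific to laboratory data.
- Protocol 9.4.3 and the opening words of SAP 3.4 allow the SAP to specify something else, and SAP 4.4.3 does so.
- SAP 3.6 records changes as small as renaming the long-term period to mid-term and dropping one SAE severity table. It does not mention laboratory data.
- Result: the SAP was allowed to choose listings, but the choice departs from the general rule and is neither declared nor justified.

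**2. How much is left without a summary?**
- Analytes in Protocol 8.1.4: 11 haematology + 3 coagulation + 18 biochemistry = 32. Screening serology is not counted.
- Mandatory visits: 4 (1 before implant, 3 after). Patients: 10.
- 32 x 4 x 10 = 1,280 values with complete data, of which 32 x 3 x 10 = 960 are post-implant.
- Per analyte: 4 x 10 = 40 values.

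**3. Could a shift escape out-of-range flags yet show in a summary? (illustration only)**

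Assumptions not in the documents: values are normal with SD 1 and centred on the reference mean, the reference range is +/-1.96 SD, and all 10 patients shift upward by s. The chance that one patient exceeds the upper limit is p = 1 - Phi(1.96 - s). The expected number flagged is 10p, and the chance that none is flagged is (1 - p)^10. The last column is the noncentral-t probability (9 df) that a 95% CI on the mean change excludes zero when the SD of the change is 1.

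| Shift s (SD) | p | Expected flagged of 10 | Chance none flagged | 95% CI on mean change excludes 0 |
|---|---|---|---|---|
| 0.5 | 0.072 | 0.7 | 47% | 29% |
| 1.0 | 0.169 | 1.7 | 16% | 80% |
| 1.5 | 0.323 | 3.2 | 2% | 99% |

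The SD of the change depends on the within-patient correlation r: SD = sqrt(2(1 - r)), which is 1.41 at r = 0, 1.00 at r = 0.5 and 0.71 at r = 0.75. For s = 1.0 the last column runs from 51% (SD 1.41) through 80% to 98% (SD 0.71).

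The half-width of the 95% CI on mean change is t(0.975, n-1)/sqrt(n), in units of the SD of the change: 0.72 for n = 10 and 0.84 for n = 8. SAP 3.4 already includes a 95% CI on the mean in its standard summary. These figures describe precision; they are not a proposed test.

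**The case against.** The strongest defence is that the SAP did what the protocol let it do. The protocol delegates secondary methods, the SAP default yields to specific text, and the endpoint asks only for a description. In a 10-patient study the 40 values for one analyte can be read by eye. Local radiology, physical examination and ECG are also only listed. All of this is true. It removes any claim of a broken laboratory-specific promise, but it does not explain why one part of the endpoint is tabulated and the other is not. Those other listed items are also not named in that endpoint.

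Three stronger readings are tempting, and the documents do not support them:
- **A reader might infer that a shift would go unreported, or that the endpoint cannot be answered.** Every value is listed, clinically significant abnormalities are recorded as adverse events (Protocol 8.1.4 and 8.1.7), and treatment-emergent ones enter the tables in SAP 4.4.1. The SAP's lists of collected laboratory fields are redacted, so it cannot be ruled out that the listings carry range flags or are ordered to show change within a patient.
- **A reader might take all 10 patients moving the same way as strong evidence of an effect.** For one analyte at one visit, with up and down equally likely, that chance is 2 x 0.5^10 = 0.00195. But 32 analytes x 3 post-screening visits give 96 comparisons. If these were independent, the chance of at least one unanimous pattern is 1 - (1 - 0.00195)^96, about 17%. The equal-chance assumption is also doubtful in patients screened with an acute fracture and then operated on.
- **A reader might credit a shift to NVDX3.** There is no control arm, so injury, surgery and recovery cannot be separated from the product.

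One objection changes the remedy. Protocol 6.1.3 treats discharge as the reference for safety, and SAP 1.3.2.1 starts the endpoint window at implant surgery, so change from screening cannot be adopted without comment.

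**Conclusion.** The point holds as a minor reporting gap that is cheap to close. Laboratory data are part of a named secondary safety endpoint, yet they get no summary while vital signs do, and SAP 3.6 does not declare the departure from the general rule. About 1,280 values at mandatory visits (complete data, 10 patients, 32 analytes) would be listed without one table, so a consistent sub-clinical shift could be missed. Under the stated assumptions, a uniform 1 SD shift would put about 1.7 of 10 patients above range, with a 16% chance that none is flagged, whereas a change summary would usually show it (51% to 98% over the correlations tried).

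The analyte count comes from Protocol 8.1.4, because the SAP's own lists are redacted. The SD-based figures are illustrative. Any summary would be descriptive only. The primary endpoint is not affected.

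**What to change.** In SAP 4.4.3, for screening, HD, W2 and W6, add:
- by-visit descriptive statistics for each analyte, in the SAP 3.4 format;
- change from a defined laboratory baseline;
- a low/normal/high shift table against that baseline.

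Add a laboratory baseline to SAP 3.5. Screening is the only scheduled pre-implant sample, whereas HD already follows the implant. State the choice and reconcile it with Protocol 6.1.3 and with the endpoint window in SAP 1.3.2.1. Keep the M3, M6 and M12 results as listings: they are triggered by suspicion, so by-visit statistics would describe a selected subset. Add a sentence that the tables are descriptive and do not support attribution to NVDX3.

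If the sponsor prefers listings only, declare and justify that in SAP 3.6. If the SAP is already final, describe and justify any change to it in the clinical study report, as the SAP introduction requires. The cost is a few standard tables from data already collected, with no extra sampling.

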4.4.4 Vital Signs

Descriptive statistics at every scheduled visit will be provided for:

- Height (cm)
- Weight (kg)
- BMI (kg/m²)
- Body temperature (°C)
- Pulse rate (beats/min)
- Respiratory rate (breaths/min)
- Mean systolic blood pressure (mmHg)

- Mean diastolic blood pressure (mmHg)

4.4.5 Physical Examination

These data will be listed.

4.4.6 TriPLICATE 12-Lead ECG

These data will be listed.

4.4.7 Pregnancy Test

These data will be listed.

4.5 Concomitant Treatments

4.5.1 Concomitant Medications

Medication that ends on the date of surgery will be considered as concomitant. Prior medication will only be these medications clearly stopping before the date of surgery.

A table will be provided showing frequency distributions of patients taking concomitant medication by anatomical class and therapeutic class for the SAF.

A listing will be provided for all medications.

A separate listing will be provided for pain medications.

In both listings it will be indicated whether the medication started before or after the start time of surgery.

4.5.2 Concomitant Therapy

These data will be listed.

4.6 Sample Description

4.6.1 Disposition of Patients

The following information will be provided:

- Number of patients in each analysis set and at each visit.
- Date of first and last inclusion visit (signing informed consent) and date of last study visit for each analysis set.
- Descriptive statistics for study duration.
- Frequency distributions of premature study discontinuation and its reason for each analysis set.

4.6.2 Protocol Deviations

A table will be provided showing frequency distributions of patients with major protocol deviations, total and broken down by type of deviation.

A listing will be provided of all protocol deviations.

5 Overview of Assessments

Screening	Acute safety FU				Long-term safety FU				Early Termination ETV		
	V1	V2 ¹	V3	V4	V5	W2	W6	M3	M6	M12	
Implant Surgery IS (Max 7 days after DRF diagnosis)					IS+13d ± 2d	IS+42d ± 7d	IS+90d ± 15d	IS+180d ± 30d	IS+360d ± 30d		
Informed consent	x									x ⁹	x ⁹
Eligibility criteria	x										
Demography	x										
Medical and concomitant medication history	x										
Index fracture evaluation/classification	x										
Physical examination	x		x		x	x	x	x	x	x	x
Weight/Height (BMD) ⁸	x		x		x	x	x	x	x	x	x
Triplane 12-Lead ECG	x		x		x	x	x	x	x	x	x
Vital signs	x		x		x	x	x	x	x	x	x
Inspection of the skin of the affected arm ⁷	x		x		x	x	x	x	x	x	x
Standard safety laboratory ³	x		x		x	x	x	x	x	x	x
Serology (HTV, HBV & HBC)	x		x		x	x	x	x	x	x	x
Pregnancy test ¹	x		x		x	x	x	x	x	x	x
Implant Surgery (IS)			x ⁵								
Peri-operative IS related information		x									
Grip strength test			x		x	x	x	x	x	x	x
NRS-pain	x		x		x	x	x	x	x	x	x
PRWE			x		x	x	x	x	x	x	x
MMWS			x		x	x	x	x	x	x	x
Radiological efficacy ⁶	AP/LAT X-ray DECT-scan	x ⁸ *(Normal CT)	x ^{7#}	x ^{7#}	x ^{7#}	x ^{7#}	x ^{7#}	x ^{7#}	x ^{7#}	x	x
AE/SAE collection			x		x	x	x	x	x	x	x
Concomitant medication			x		x	x	x	x	x	x	x
Concomitant therapy			x		x	x	x	x	x	x	x

1 In-clinic stay. The patient may be hospitalized before the surgery following to hospital standard of care. The required pre-operative assessments can be done up to 3 days before the surgery.

2 Skin inspection to evaluate potential surgical site infections.

3 At screening, Discharge, V4 and V5: safety laboratory analyses are mandatory. At V6, V7 and V8: Upon occurrence or any suspicion of safety related issues.

4 In women of childbearing potential only: a serum pregnancy test will be performed at Screening and at V8

5 Follow the instructions ad per "NVDX 3 handling Manual".

6 To guarantee image quality, all X-rays and CT-scan acquisitions will need to strictly follow the imaging instructions as described per "Imaging Acquisition Manual".

7 AP/LAT X-rays: both after insertion of fixation device, and after insertion of the NVDX3 implant (at the end of the surgery)

8 Height at screening only

9 Informed consent proposing participation to the long-term safety follow-up study (NVDX3-CLNOX)

*

Standard of care image acquisitions for the diagnosis and follow-up of DRF
